**Table 4.PR Interval Prolongation Management**

Toxicity	Not Symptomatic	Symptomatic
1 st -Degree Heart Block (PR interval >200 msec)	No dose hold or reduction needed. Assess concomitant medications. Monitor closely by obtaining pre-dose ECG at next visit, even if unscheduled. Instruct patient to call if	Withhold dose. Assess concomitant medications. Obtain ECG in approximately 48 hours and re-assess symptoms and PR-interval. Restart at
2 nd -Degree Heart Block	Withhold dose. Assess concomitant medications. Repeat ECG in approximately 48 hours. Instruct patient to call if symptoms develop that may be related to heart block. Restart at same dose or consider dose reduction if subsequent ECG does not show	Withhold dose. Refer for cardiac observation and monitoring. Consider pacemaker placement if symptomatic heart block persists. Resume at reduced dose only when symptoms resolve AND 2nd degree
Complete Heart Block	Withhold dose. Refer for cardiac observation and monitoring. Temporary pacemaker placement may be indicated for severe symptoms associated with heart block. If heart block does not resolve, placement of a permanent pacemaker may be considered. If pacemaker placed, may resume at full dose.	

Study treatment could be interrupted for Grade 3, Grade 4, or intolerable Grade 2 toxicity (using NCI CTCAE v5.0). Upon recovery to Grade 2 or baseline, and in the clinical judgment of the investigator with the agreement of the patient, the treatment could be resumed as follows:

- For interruption due to Grade 3 or intolerable Grade 2 toxicity, treatment could be resumed at the same dose level or reduced per protocol.
- For episodes of Grade 4 toxicity, reduction to the next dose level was highly recommended.

For patients whose study treatment had been interrupted due to treatment related toxicity as described above, treatment was permanently discontinued if they failed to recover within 2 weeks of dose interruption, unless there was discussion of the clinical circumstance with the Sponsor and agreement that the patient could resume treatment after a lapse of >2 weeks.

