**Table 3. Lorlatinib Dose Modifications for Lorlatinib-Related Toxicities Non-Hematologic Toxicities**

Toxicity	Grade** 1	Grade 2**	Grade 3	Grade 4
Pancreatitis	NA	If elevated enzymes (both amylase and lipase are Grade $\leq 2$ ) are observed in the absence of radiological findings of pancreatitis: continue lorlatinib at the same dose level without dose hold. Repeat lipase and amylase and obtain pancreatic isoenzyme if possible. If radiologically confirmed pancreatitis: withhold lorlatinib dose. Repeat radiology and lipase and amylase weekly and obtain pancreatic isoenzyme. If appropriate, resume lorlatinib treatment at one dose level lower if radiology has returned to baseline and lipase and amylase are Grade $\leq 2$ .	Permanently discontinue lorlatinib.	Permanently discontinue lorlatinib.
Pneumonitis (in the absence of disease progression, pulmonary embolism, positive cultures or radiation effect)§.	Asymptomatic, radiographic findings only: No need for lorlatinib dose adjustment. Initiate appropriate monitoring.	Withhold current lorlatinib dose until toxicity has returned to baseline. Rule out infection and consider initiating treatment with corticosteroids. Then resume lorlatinib treatment at one dose level lower. Discontinue lorlatinib permanently if pneumonitis recurs or if failure to recover after 6 weeks of study treatment hold and steroid treatment.	Permanently discontinue lorlatinib.	Permanently discontinue lorlatinib.
Electrocardiogram QTc prolongation .	Assess electrolytes and concomitant medications. Correct any electrolyte abnormalities, or hypoxia. Continue lorlatinib at the same dose level.	Assess electrolytes and concomitant medications. Correct any electrolyte abnormalities, or hypoxia. Continue lorlatinib at the same dose level.	Withhold lorlatinib dose. Assess electrolytes and concomitant medications. Correct any electrolyte abnormalities, or hypoxia. Upon recovery to Grade $\leq 1$ resume lorlatinib treatment at one dose level lower.	Permanently discontinue lorlatinib.
LV Dysfunction	CTCAE v5.0 does not report Grade 1.	CTCAE v 5.0 does not report Grade 2.	Permanently discontinue lorlatinib.	Permanently discontinue lorlatinib.

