Non-Hematologic General	Continue lorlatinib at the same dose level.	Continue lorlatinib at the same dose level.	Withhold lorlatinib dose until toxicity is Grade $\leq 1$ (or has returned to baseline) then reduce the dose by 1 level or rechallenge at the same dose.*	Withhold dose until toxicity is Grade $\leq 1$ (or has returned to baseline), then reduce the dose by 1 level* or

			discontinue at the discretion of the investigator.																									

* Patients who develop asymptomatic Grade 4 hyperuricemia or Grade 3 hypophosphatemia may continue lorlatinib without dose modification at the discretion of the investigator. Nausea, vomiting or diarrhea must persist at Grade 3 or 4 despite maximal medical therapy to require lorlatinib dose modification .
 
** In cases where no specific dose adjustments for Grade 1 or Grade 2 treatment-related toxicity are provided, investigators should always manage their patients according to their medical judgment which may include dose reduction or interruption based on the particular clinical circumstances.
 
§ If a patient has a potential diagnosis of pneumonitis or drug-related lung injury the same evaluations/procedures provided should be considered to assist or exclude the diagnosis of pneumonitis during this period.
																												

Hematologic Toxicities
																												

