Toxicity	Grade 1	Grade 2	Grade 3	Grade 4																								
Hematologic General	Continue lorlatinib at the same dose level.	Continue lorlatinib at the same dose level.	Withhold lorlatinib dose until toxicity is Grade $\pm 1$ (or has returned to baseline), then rechallenge at the same dose or reduce the dose by 1 dose level.	Withhold lorlatinib dose until toxicity is Grade $\pm 1$ (or has returned to baseline) then rechallenge at the same dose or reduce the dose by 1 dose level.																								
Lymphopenia	Continue lorlatinib at the same dose level.	Continue lorlatinib at the same dose level.	If no evidence of infection or other clinically significant toxicity, continue lorlatinib at the same dose; otherwise, withhold dose until toxicity is Grade $\pm 1$ (or baseline) then rechallenge at the same dose or reduce by 1 level.	If no evidence of infection or other clinically significant toxicity, continue lorlatinib at same dose; otherwise, withhold dose until toxicity is Grade $\pm 1$ (or baseline), then rechallenge at the same dose or reduce the dose by 1 dose level.																								

Lipid Elevation Toxicities
																												
Cholesterol	Continue lorlatinib at the same dose. Consider introducing use of a statin or other lipid lowering agent as	Introduce the use of a statin or other lipid lowering agent as appropriate, and continue lorlatinib at the same dose.	Introduce the use of a statin or other lipid-lowering agent as appropriate, or increase the dose of the statin/lipid lowering agent	Increase the dose of the statin or other lipid-lowering agents, or change to a new statin/lipid lowering agent. Withhold lorlatinib dose until toxicity is																								

	appropriate based on investigator's medical judgment.		or change to a new agent. Either continue lorlatinib at the same dose without interruption or withhold dose until toxicity is	Grade $\leq 2$ and then reduce the dose by 1 dose level or rechallenge at the same dose.

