Triglycerides	Continue lorlatinib at the same dose. Consider introducing use of a statin or other lipid-lowering agent as appropriate based on investigator's medical judgment.	Introduce the use of a statin or other lipid-lowering agent as appropriate, and continue lorlatinib at the same dose.	Introduce the use of a statin or other lipid-lowering agent as appropriate, or increase the dose of the statin/lipid-lowering agent or change to a new agent. Either continue lorlatinib at the same dose without	Increase the dose of the statin or other lipid-lowering agents, or change to a new statin/lipid-lowering agents. Withhold lorlatinib dose until toxicity is Grade $\leq 2$ and then reduce the dose by 1 dose level or rechallenge at the same dose.

CNS Toxicities				
Toxicity	Grade 1	Grade 2	Grade 3	Grade 4
CNS effects β	Continue lorlatinib at the same dose or withhold dose until recovery to baseline.	Continue lorlatinib at same dose or withhold dose until recovery to Grade $\leq 1$ . Consider dose reduction or rechallenge at the same dose.	Withhold lorlatinib dose until toxicity is Grade $\leq 1$ . Reduce dose to the next lower dose.	Permanently discontinue lorlatinib.

β Examples of CNS effects could include changes in speech, memory, sleep, cognition, or vision.

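### The general interruption text closing Section 5.4 conflicts with Table 3 on dose after resumption and with Section 5.2 on hold length, and nothing says which governs

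*Protocol*

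**What the plan says.** Three parts of the Protocol tell a site what to do after an interruption for toxicity.

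**Section 5.4, text after Table 4.** It sits under the PR-interval heading, but its opening sentence covers any Grade 3, Grade 4 or intolerable Grade 2 toxicity by CTCAE grade. Its rule for the lower grades is "For interruption due to Grade 3 or intolerable Grade 2 toxicity, treatment could be resumed at the same dose level or reduced per protocol". For the highest grade it says "For episodes of Grade 4 toxicity, reduction to the next dose level was highly recommended". A patient who has not recovered within 2 weeks of interruption stops for good, unless the case is discussed with the Sponsor and resumption is agreed.

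**Section 5.2 and Table 3.** Several rows direct "Permanently discontinue lorlatinib". For Grade 3 QTc prolongation the instruction is "Upon recovery to Grade $\leq 1$ resume lorlatinib treatment at one dose level lower", and for Grade 3 CNS effects "Withhold lorlatinib dose until toxicity is Grade $\leq 1$ . Reduce dose to the next lower dose". The text after Table 2 ends lorlatinib if a significant toxicity has not recovered within 42 days, or sooner if the investigator judges it severe enough. It mentions no Sponsor agreement for continuing a hold. Section 5.2 introduces Table 3 as recommendations.

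**Section 6.4.8.** A dose interruption of more than 2 consecutive weeks calls for a discussion with the investigator.

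Section 5.5 also bears on pulmonary events. If drug-induced interstitial lung disease is a concern, treatment stops until the patient is evaluated, and it may resume once treatment-induced pulmonary toxicity has been excluded.

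No sentence ranks these texts.

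**The concern.** Rules on restarting a drug after severe toxicity should give one answer at every site, and the synopsis lists six sites. Here an investigator who follows the end of 5.4 may restart lorlatinib at full dose after a Grade 3 QTc or CNS event, while one who follows Table 3 would lower the dose. A site could also take the 5.4 text as leave to resume after events for which Table 3 ends treatment.

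On holds, one site may stop permanently just after day 14, another may seek Sponsor agreement, and a third may wait until day 42. At stake are the safety of the patients concerned and consistent handling of exposure.

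**Working it through.** No sample-size, power or alpha figure is involved, so the check sets the rules side by side and scales the differences.

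**1. Scope of the 5.4 text.** Table 4 is organised by degree of heart block and by symptoms. The text after it is organised by CTCAE grade and refers to treatment-related toxicity in general. It therefore reads as a general rule placed under a specific heading.

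**2. Dose on resumption after Grade 3.**

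| Event | Text after Table 4 | Table 3 |
|---|---|---|
| QTc prolongation, Grade 3 | same dose or reduced | one dose level lower |
| CNS effects, Grade 3 | same dose or reduced | next lower dose |

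Table 2 gives the levels as 100, 75 and 50 mg once daily. From 100 mg, the 5.4 text permits 100 mg where Table 3 gives 75 mg: 100 / 75 = 1.33, a dose one third higher. From 75 mg the comparison is 75 / 50 = 1.5. In these two cells the same-dose option directly contradicts Table 3. The general non-hematologic and hematologic Grade 3 rows allow either the same dose or a lower one, so there is no dose conflict there.

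**3. Permanent discontinuation.** Table 3 directs it in these cells:

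- pancreatitis, Grades 3 and 4: 2
- pneumonitis, Grades 3 and 4: 2
- LV dysfunction, Grades 3 and 4: 2
- QTc prolongation, Grade 4: 1
- CNS effects, Grade 4: 1

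The total is 2 + 2 + 2 + 1 + 1 = 8. The 5.4 text names no exception for any of them. Its Grade 4 sentence recommends a dose reduction, which presupposes that treatment can resume. The two pneumonitis cells are partly protected, because Section 5.5 separately blocks resumption unless treatment-induced toxicity is excluded. The other six have no such second text.

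**4. Length of hold.**

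| Source | Trigger | Consequence |
|---|---|---|
| 5.4, after Table 4 | no recovery within 2 weeks | permanent stop unless the Sponsor agrees |
| 5.2, after Table 2 | no recovery within 42 days | permanent stop |
| 6.4.8 | interruption over 2 consecutive weeks | discussion with the investigator |

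Section 6.4.8 shares the 2-week trigger with 5.4 and differs in consequence and decision-maker. The numerical difference is between 5.4 and 5.2: 42 - 14 = 28 days. Section 5.1 sets a course of 6-8 weeks, or 42-56 days:

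- 14 days: 14/42 = 33%, 14/56 = 25%
- 42 days: 42/42 = 100%, 42/56 = 75%
- 28-day gap: 28/42 = 67%, 28/56 = 50%

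Table 3 also allows Grade 2 pneumonitis a 6-week hold, although the 5.4 text covers intolerable Grade 2 events with its 2-week limit.

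**The case against.** The strongest reply is that specific rules override general ones. An investigator facing Grade 3 pancreatitis would look up the pancreatitis row, find permanent discontinuation, and never reach a rule about resuming from an interruption. The 5.4 text is also permissive, leaves the decision to clinical judgment, and refers to reducing per protocol, which can be read as a pointer to Table 3. Section 5.2 itself calls Table 3 recommendations. The hold rules can be followed together: discuss at 2 weeks, continue only if agreed, stop at 42 days.

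Much of this stands. The eight discontinuation cells are reconcilable on that reading, and so are the hold rules. But the protocol states neither reading. The reference to reducing per protocol comes after the same-dose option and leaves it open, so the Grade 3 QTc and CNS conflict remains. If Table 3 is only advisory, there is still less reason in the text for it to prevail.

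Three stronger readings are tempting and should not be drawn:

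- **That the protocol lets a site restart freely after Grade 3 pneumonitis.** Section 5.5 stands in the way.
- **That 5.4 sets a laxer recovery grade.** The text reads "Upon recovery to Grade 2 or baseline, and in the clinical judgment of the investigator", against Grade 1 or lower in several Table 3 rows. A patient held for Grade 2 cannot recover to Grade 2, and comparison signs are damaged nearby, as in "Withhold lorlatinib dose until toxicity is Grade $\pm 1$ (or has returned to baseline), then rechallenge at the same dose". A sign may simply have been lost, so nothing here rests on that wording.
- **That 6.4.8 sets a third hold limit.** It sets none.

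**Conclusion.** The concern holds as a conflict of guidance with no stated precedence. It is clear in two cells (Grade 3 QTc prolongation and Grade 3 CNS effects, 100 mg against 75 mg). In eight more cells it is an unresolved ambiguity, with pneumonitis already guarded by Section 5.5. On holds, 2 weeks unless the Sponsor agrees and 42 days are not reconciled anywhere, which leaves 28 days open to different handling.

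The text does not order anyone to restart. The percentages are limits of the rules for one patient. The protocol gives no basis for how often such events or long holds will occur among the 25 patients, so no expected number is claimed. A reader might infer that the primary analysis is compromised. The documents do not support that: the Simon stage sizes and cut-offs, and the error rates that follow from them, do not depend on these rules. The point should be fixed because it concerns safety and the correction is cheap.

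**What to change.** 1. Delete the text after Table 4, from its opening sentence on interrupting study treatment to the end of 5.4. Confining it to PR prolongation would not work: Table 4 lets symptomatic second-degree block resume only at a reduced dose, which the same-dose option would contradict.
2. State in 5.2 that Table 3 governs recovery grade, dose on resumption and permanent discontinuation, with Table 4 governing for PR prolongation and Section 5.5 applying to pulmonary toxicity.
3. State one hold rule in identical words in 5.2 and 6.4.8: a hold over 2 weeks needs documented Sponsor agreement before restart, and lorlatinib is permanently discontinued if toxicity has not recovered by 42 days. Add that Table 3's immediate permanent discontinuations still apply.

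The cost is a wording amendment to 5.2, 5.4 and 6.4.8, plus a record of Sponsor agreement for each hold over 2 weeks. The 5.4 text already asks for that agreement. No visits, tests or patients are added.

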**Table 2. Lorlatinib Dose Modification**

Dose Levels	Lorlatinib Dose
0	100 mg QD
-1	75 mg QD
-2	50 mg QD
Dose reductions below dose level -2 are not allowed.	

Patients will be monitored closely for toxicity, and the dose of lorlatinib may be adjusted as indicated in Table 2. Dose reduction by 1 and, if needed, 2 dose levels will be allowed depending on the type and severity of toxicity encountered.

If a patient has a significant toxicity from lorlatinib treatment which fails to recover within 42 days (6 weeks) or, in the opinion of the investigator, requires permanent

discontinuation of the treatment based on the severity of the adverse event, then this patient should not be further treated with lorlatinib but should remain in the trial with ongoing tumor assessments until the end of study

Recommendations for lorlatinib dose modification for treatment-related non-hematological and hematological toxicity, as well as for treatment-related toxicity of special interest, are provided in Table 3 below.

Re-escalation is not allowed except if discussed with and approved by the sponsor's medical contact.

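### The general resumption text after Table 4 makes no exception for the eight event-grade combinations that Table 3 marks for permanent discontinuation, and the protocol does not say which text governs

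*Protocol*

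**What the plan says.** Two parts of Section 5 cover what happens to lorlatinib after a severe toxicity.

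- **Section 5.2, Table 3.** The lead-in reads: "Recommendations for lorlatinib dose modification for treatment-related non-hematological and hematological toxicity, as well as for treatment-related toxicity of special interest, are provided in Table 3". In the rows for named events the entry is "Permanently discontinue lorlatinib" for pancreatitis, pneumonitis and LV dysfunction at both Grade 3 and Grade 4, for QTc prolongation at Grade 4, and for CNS effects at Grade 4. A general non-hematologic row allows a hold followed by dose reduction or rechallenge at Grade 3, and a hold followed by reduction or discontinuation at Grade 4.
- **Section 5.4, text after Table 4.** Table 4 deals with PR prolongation by degree of heart block and symptoms. The text beneath it changes to CTCAE grades: "Study treatment could be interrupted for Grade 3, Grade 4, or intolerable Grade 2 toxicity (using NCI CTCAE v5.0". After recovery, and subject to the investigator's judgment, "with the agreement of the patient, the treatment could be resumed as follows". Two rules follow: "For interruption due to Grade 3 or intolerable Grade 2 toxicity, treatment could be resumed at the same dose level or reduced per protocol" and "For episodes of Grade 4 toxicity, reduction to the next dose level was highly recommended".

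Section 5.5 deals separately with suspected drug-induced lung toxicity. Treatment stops for evaluation, dose modification is said not to be appropriate, and treatment may resume where investigation has ruled out a treatment-induced cause.

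**The concern.** The Table 3 entries for the named events are unconditional. The text after Table 4 is general in scope and carries no exception for them. A site treating a recovered patient with, say, Grade 4 QTc prolongation can find a bar in one place and a permission in the other.

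These are the events the protocol itself singles out for permanent stopping, in patients who are due for lung surgery, and six sites will be reading the text. Safety and tolerability is a secondary endpoint. If sites resolve the ambiguity differently, exposure and the recorded reason for stopping would reflect the site's reading as well as the drug's tolerability.

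The question here is whether resumption is allowed at all after these events. How long a hold may last, and to what grade the toxicity must recover, are separate mismatches in the same paragraph. They matter here mainly because they show that the paragraph was not written to defer to Table 3.

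**Working it through.** No sample size, error rate or other statistical figure is involved, so the check sets the passages side by side.

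**Step 1: Table 3 against the text after Table 4, for the five rows containing a permanent stop.**

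| Event | Table 3, Grade 3 | Table 3, Grade 4 | Text after Table 4 |
|---|---|---|---|
| Pancreatitis | stop permanently | stop permanently | may resume after either grade |
| Pneumonitis | stop permanently | stop permanently | may resume after either grade |
| LV dysfunction | stop permanently | stop permanently | may resume after either grade |
| QTc prolongation | hold, then resume one level lower | stop permanently | may resume after either grade |
| CNS effects | hold, then next lower dose | stop permanently | may resume after either grade |

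Count of permanent-stop cells: 2 + 2 + 2 + 1 + 1 = 8. Grade 3 QTc prolongation and Grade 3 CNS effects are not counted, because Table 3 itself allows resumption there.

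**Step 2: is the text after Table 4 limited to PR prolongation?** Its position suggests so, but its wording does not. Table 4 already gives restart instructions by degree of block and symptoms. The text below it drops that classification, refers to toxicity by CTCAE grade, and then speaks of treatment-related toxicity in general.

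**Step 3: is precedence stated?** Section 5.2 describes Table 3 as recommendations. Its opening sentence lets investigators use local supportive-care practice or follow the guidance given. The text after Table 4 does not mention Table 3's permanent-stop cells. No sentence ranks one over the other.

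**Step 4: does the text after Table 4 behave like a summary of Section 5.2?** It does not, on two further points.

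- *Recovery level for resuming.* Table 3's general non-hematologic row requires Grade 1 or lower, or baseline. The text after Table 4 requires Grade 2 or baseline.
- *Hold window.* Section 5.2 bars further lorlatinib when a significant toxicity fails to recover "within 42 days (6 weeks) or, in the opinion of the investigator, requires permanent" discontinuation. The text after Table 4 says "treatment was permanently discontinued if they failed to recover within 2 weeks of dose interruption", unless the sponsor agrees otherwise. That is 14 days against 42.

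A paragraph that only restated Section 5.2 would carry the same recovery level and window. This one reads as a separate rule set.

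**The case against.** The strongest reply is that specific rows override general text. Table 3 already needs that reading internally: its general non-hematologic row permits resumption after Grade 3 and Grade 4 and names no exceptions either, yet it sits beside rows that stop treatment permanently. Extending the same reading to the text after Table 4 removes the conflict. This is a reasonable inference and probably what most investigators would do. It is weaker outside the table than inside it, because the later text stands in another section, sets its own terms and does not refer back.

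Second, the text is permissive. It says treatment could be resumed, subject to judgment and agreement, so a site that follows Table 3 breaks nothing in it. That stands: rechallenge is allowed, not required. A permission and an unconditional bar for the same event still need to be reconciled.

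Third, other provisions limit the risk. For the two pneumonitis cells, Section 5.5 ties resumption to excluding a treatment-induced cause, which supports the stop for drug-related lung toxicity. Section 5.2 ends treatment when the investigator judges that severity requires it, and Sections 5.1 and 6.4.8 do so for unacceptable toxicity. These points stand, but apart from Section 5.5 they rest on individual judgment, and none states precedence.

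A reader might infer more: that the protocol directs rechallenge after these events, or that the trial's results are materially distorted. The document supports neither. One patient in 25 is 4 percentage points of any proportion, but a discontinuation rate is not a defined endpoint, no frequencies are given for the eight combinations, and treatment lasts only 6 to 8 weeks.

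**Conclusion.** The point holds as an unresolved inconsistency in the dose-modification instructions. In eight event-grade cells Table 3 stops lorlatinib permanently, while the general text after Table 4, read as written, leaves resumption open. The sensible reading favours the event-specific rows, and for drug-induced lung toxicity Section 5.5 backs it, but the protocol leaves this to inference.

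The conclusion rests on two readings: that the text after Table 4 is not confined to PR prolongation, which its wording supports, and that no precedence rule exists elsewhere in the protocol, where none was found. The main consequence is for the clarity of a safety instruction. Any effect on tolerability results or on pCR is possible but cannot be sized from the document. It should be corrected, though it does not undermine the trial's design.

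**What to change.** Amend Section 5 so that the text after Table 4, Table 3 and Section 5.5 agree:

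1. State which text governs when they differ.
2. State whether, and if so how, the resumption text applies to the events that Table 3 marks for permanent discontinuation. If it is meant only for certain toxicities, name them.
3. In the same amendment, reconcile that paragraph's recovery level and hold window with Section 5.2 and Table 3.

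Which clinical rule applies is for the sponsor to decide, and none is proposed here. The cost is a wording change in one protocol amendment, with no added patients, visits or procedures.
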